## 1 OBJECTIVES OF THE STUDY

### 1.1 Primary Objective

The primary objective is to evaluate the **tolerance and safety** of TACE with TANDEM™ 100 $\mu$  microspheres preloaded with doxorubicin, describing:

- Appearance and intensity of post-embolization syndrome in the 1st week after treatment
- Major adverse events during the 30 days after TACE.
- Minor adverse events during the 30 days after TACE.
- Mortality derived from treatment.

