### **3.4 Expected number of participants and justification**

It is an observational and descriptive study. As far as we know, no data have been published in the literature on the proportion of adverse effects / complications associated with the administration of QETA with 100 micron microspheres, so it has not been possible to make a sample size predetermination based on data previous. It is intended to include 10 patients per center, which would make a total of 130 patients. With this sample size, an accuracy of 1.71% can be achieved in the estimation of a proportion through a bilateral asymptotic confidence interval of 95.00%, assuming that the proportion of the event is 1.00%.

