#### **4.2 Follow-up**

After the first TACE procedure, the following evaluations will be carried out:

1. Clinical and analytical control 10-20 days after discharge according to usual practice: Clinical visit in which the general condition of the patient is assessed and will be asked whether or not he had Sd. Post-pay, its duration and intensity. Analytical including blood count, coagulation tests, basic biochemistry, transaminases and bilirubin. The study may be extended with more complete imaging or analytical tests if the physician considers it necessary.
2. Dynamic liver CT or MRI every 3 m for the first 6 months and then twice a year according to usual practice.
3. Clinical and laboratory review every 3 m the first 6 months and then twice a year as usual practice until the progression, death or loss of patient follow-up, with a maximum of 5 years.
  - a. Quality of life assessment (ECOG)
  - b. Laboratory assessment
  - c. Evaluation of safety and efficacy and assessment of retreatment if appropriate.

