### **5 TUMOR RESPONSE ASSESSMENT**

#### **5.1 Study Variables**

Related to the patient and the disease: age, gender, etiology of liver disease, diagnosis of HCC, previous nodules treated with surgery, ablation or TACE, Child-Pugh score, BCLC stage of the tumor, size, location and number of patients. nodules, segmental vascular

invasion of the portal vein, bilioenteric shunt or previous biliary prosthesis, carrier of porto-systemic shunt, relevant concomitant pathologies.

- Variables related to the primary objective:

**Post-embolization syndrome:** in an adverse effect of TACE that is defined as a picture of abdominal pain, fever  $<38.5^{\circ}\text{C}$ , and variable degree leukocytosis that appears 24 hours after the procedure and can last up to 10 days. It can be accompanied by nausea, vomiting and asthenia. It is related to tissue necrosis and is self-limited, its treatment is symptomatic. Its incidence is variable and linked to the volume of necrotic tissue.

**Early adverse events** derived from the procedure during the first 30 days:

1. Liver failure defined by ascitic decompensation with elevation of serum Br, jaundice and transaminases  $>x5$  and / or hepatic encephalopathy.
2. UGIB of peptic or varicose origin
3. Intense pain that requires continued iv medication
4. High fever that is not justified by Sd. post refund
5. Liver abscess
6. Coagulative portal thrombosis
7. Acute pancreatitis
8. Acute cholecystitis
9. Renal failure, elevation of serum Cr  $\times 2$  its baseline value.
10. Pleural effusion

**Late adverse events** arising from the procedure between the first 30 days and 6 months:

1. Intrahepatic bile duct injury defined by dilation of biliary radicals with cholestatic symptoms.

Additional therapies against cancer (sorafenib, radioembolisation, symptomatic treatment) will be documented for all patients every three months until death.

**Mortality** in the first 30 days after treatment

- Variables related to secondary objectives: the information will be obtained from imaging studies performed interchangeably with liver MR or CT using intravenous contrast and performing three-phase dynamic studies (arterial, portal and balance phase). Imaging studies will be evaluated according to RECIST 1.1 criteria.

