## 6 STATISTICAL ANALYSIS PLAN

### 6.1 Statistic analysis

A descriptive analysis of the variables included in the study will be carried out. Descriptive statistics will be calculated, including frequencies and percentages for categorical variables and means  $\pm$  standard deviations or medians with interquartile ranges for continuous variables. Univariate analysis is planned to identify variables related to developing complications, using Chi-square tests. To identify risk factors related to mortality, univariate logistic regression models will be constructed. For survival analysis, Kaplan-Meier curves will be plotted, and log-rank tests are going to be used to evaluate differences between the curves. A column graph graft creation is planned to show the tumor response. In all cases where possible, the 95% confidence interval significant at  $p<0.05$  will be calculated. All effects are considered. All statistical analysis will be performed with the SAS 9.4 (SAS Institute Inc., Cary, NC, USA).

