### 7.3 Severity assessment

30-day mortality, minor and major adverse events after Tandem-100 DEB-TACE were assessed in accordance with CTCAE 4.03 criteria (33)

The maximum intensity should be assigned one of the following categories:

- **Minor:** An adverse event easily tolerable by the subject, causing minimal discomfort and not interfering with daily activity.
- **Major:** Any adverse event or adverse reaction that, at any dose, causes death, threatens the life of the subject, necessitates hospitalization or prolongation of the subject, causes permanent or significant disability or disability, or results in an anomaly or congenital malformation. For the purposes of its notification, suspicions of adverse events or adverse reactions that are considered medically important will be treated as serious, even if they do not meet the above criteria.

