## 8.3 Patient information

The researcher must explain to each subject the nature of the study, its purposes, procedures, expected duration and the potential risks and benefits related to participation in the study, as well as any inconvenience this may entail. Each participant should be advised that their participation in the study is voluntary and that they can leave the study at any time, without affecting their subsequent medical treatment, or their relationship with the treating doctor.

Informed consent will be provided by standard writing, in language easily understood by the participant. The subject must have sufficient time to read and understand the explanations before dating and signing the informed consent and should receive a copy of the signed document. No subject can be included in the study without previously giving their informed consent.

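### Section 6.1 models mortality risk factors by logistic regression without saying which mortality is meant or how incomplete follow-up is handled; the method serves poorly on either reading.

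*Combined protocol and SAP*

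**What the plan says.** On risk factors for death, section 6.1 says: "To identify risk factors related to mortality, univariate logistic regression models will be constructed". It gives no horizon and no rule for patients whose vital status is unknown. The next sentence deals with survival separately: "For survival analysis, Kaplan-Meier curves will be plotted, and log-rank tests are going to be used to evaluate differences between the curves". No time-to-event regression is named.

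Elsewhere the word mortality is used in these ways:

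- Section 1.1 (Primary Objective) lists "Mortality derived from treatment", with no window.
- Section 5.1, under the primary-objective variables, defines mortality as death "in the first 30 days after treatment".
- Section 7.3 says "30-day mortality, minor and major adverse events after Tandem-100 DEB-TACE were assessed in accordance with CTCAE 4.03 criteria".
- Section 1.2 lists 2-year overall survival as a separate, secondary objective.

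On follow-up, section 4.2 runs clinical and laboratory review "until the progression, death or loss of patient follow-up, with a maximum of 5 years", whereas the Summary gives two years after the final treatment. Section 8.3 tells participants that "they can leave the study at any time". Sections 3.4 and 6.2 plan 130 patients and base precision on "assuming that the proportion of the event is 1.00" per cent.

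**The concern.** A plain logistic model needs each patient's dead-or-alive status at one common time. Section 6.1 does not name that time. Withdrawal is allowed, and the documents give two different follow-up lengths, so status at a late horizon may be unknown for some patients. The analyst would then have to improvise, and the usual improvisations (count the patient as alive, or delete the record) can each move the odds ratio.

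Restricting the analysis to 30 days removes that difficulty but may leave almost no deaths to model. In either case the study could report risk factors for death that reflect how follow-up ended, or one or two individual deaths, more than prognosis. This applies to every single-factor model and is separate from the absence of covariate adjustment.

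**Working it through.** **1. The plan's own figure.** Sections 3.4 and 6.2: n = 130, p = 0.01, two-sided 95% asymptotic interval. Half-width = 1.96 × √(0.01 × 0.99 / 130) = 1.71%. This reproduces. The documents give no figure for the logistic analysis, so the remaining steps rest on stated assumptions.

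**2. Reading A: 30-day mortality.** The only event rate in the plan is the illustrative 1%, given for the precision of an adverse-event proportion. Borrowing it for deaths:

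- Expected deaths = 130 × 0.01 = 1.3.
- Binomial(130, 0.01): P(0) = 27%, P(at most 1) = 63%, P(at most 2) = 86%.

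Loss is not the problem here. With 1% deaths without the factor, a hazard ratio of 2 and a full-follow-up odds ratio (OR) of 2.01, loss of 5% in both groups leaves the OR at 2.01. Loss of 2% against 5% gives 1.98 (coded alive) or 2.04 (dropped).

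**3. Reading B: death by 24 months.** Assumptions, none from the documents: death 35% (good prognosis) and 60% (poor prognosis), 40% of patients in the poor group, exponential times, and loss by 24 months of 10% (good) and 30% (poor) if nobody died.

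Monthly hazards:

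- Death: h = −ln(0.65)/24 = 0.01795 (good) and −ln(0.40)/24 = 0.03818 (poor).
- Loss: m = −ln(0.90)/24 = 0.00439 (good) and −ln(0.70)/24 = 0.01486 (poor).

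Observed death D = h/(h+m) × (1 − exp(−24(h+m))). Known alive at 24 months A = exp(−24(h+m)).

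- Good: A = 0.65 × 0.90 = 0.585; D = 0.8035 × 0.415 = 0.3335.
- Poor: A = 0.40 × 0.70 = 0.280; D = 0.7198 × 0.720 = 0.5183.

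Odds ratios:

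- Complete follow-up: (0.60/0.40)/(0.35/0.65) = 2.79.
- Lost coded alive: (0.5183/0.4817)/(0.3335/0.6665) = 2.15.
- Lost dropped: (0.5183/0.280)/(0.3335/0.585) = 3.25.

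Pooled mortality:

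- True: 0.6 × 0.35 + 0.4 × 0.60 = 45.0%.
- Coded alive: 0.6 × 0.3335 + 0.4 × 0.5183 = 40.7%.
- Dropped: 0.4074/(0.4074 + 0.6 × 0.585 + 0.4 × 0.280) = 0.4074/0.8704 = 46.8%.

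**4. Dependence on the loss pattern** (same death rates, OR 2.79 with complete follow-up):

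| Loss, good / poor | OR, coded alive | OR, dropped |
|---|---|---|
| 10% / 30% | 2.15 | 3.25 |
| 10% / 40% | 1.91 | 3.57 |
| 10% / 10% | 2.69 | 2.80 |
| 20% / 20% | 2.61 | 2.81 |
| 30% / 10% | 3.17 | 2.43 |

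**5. Behaviour of Cox regression.** A simulation used 1,000 runs, n = 130, half of patients with the factor, 60% 2-year survival without it, and loss of 10% without against 30% with it. Mean Cox hazard ratios were 1.01 (true 1) and 2.01 (true 2). With no true effect, the closed-form logistic OR under the same loss is 0.84 (coded alive) or 1.15 (dropped), and simulated type I error was 7.6% or 7.2% (Cox 5.8%). In this simulation loss depended only on the modelled factor. It does not show that Cox is safe when exit depends on unmeasured prognosis.

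**The case against.** The strongest reply is that the protocol does define mortality. Sections 5.1 and 7.3 tie it to 30 days, overall survival is a separate endpoint, and section 6.1 can be read as keeping that split: logistic regression for 30-day mortality, Kaplan-Meier for survival. On that reading the window is fixed and loss hardly matters. This stands. A reader might infer that the plan treats the same withdrawals in two incompatible ways, but the two methods may serve different endpoints. What remains on this reading is sparse data, together with the fact that section 6.1 does not repeat the window and section 1.1 gives none.

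Other stronger readings are tempting and are not supported:

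- That patients who leave are coded as survivors or deleted. The plan is silent; these are only the default ways of fitting a plain logistic model.
- That the odds ratios are biased, in a known direction. No loss rate is given. Equal loss moves the OR little, and heavier loss in the good-prognosis group reverses both shifts.
- That 1% is an expected death rate. It is an illustrative proportion for adverse effects.
- That progression means exit. Section 4.2 ends review at progression, but section 5.1 records further cancer therapy for all patients every three months until death. The Summary's calendar of one year's recruitment and two years' follow-up would also let every patient reach 24 months.
- That Cox regression cures prognosis-related exit. Like Kaplan-Meier, it assumes non-informative censoring.

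Sampling error also dwarfs the shift. With 130 patients fully followed (52 poor, 78 good), the standard error of the log OR is √(1/31.2 + 1/20.8 + 1/27.3 + 1/50.7) = 0.369, so the 95% interval around 2.79 is about 1.35 to 5.75. That limits the practical weight of the bias but is no reason to prefer a method that discards time at risk.

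**Conclusion.** The point holds as a gap in specification and an unsuitable choice of method, not as demonstrated bias. On the 30-day reading, about 1.3 deaths would be expected if the rate were near 1%, too few to support a risk-factor model; a materially higher rate would ease this. On the longer reading, differential loss of the assumed size moves an OR of 2.79 to 2.15 or 3.25 and apparent mortality from 45.0% to 40.7% or 46.8%. These figures depend on the assumed death rates, group split, exponential times and loss pattern. Mortality risk factors are not a listed objective and the study is descriptive, so the consequence is limited to an exploratory result. The remedy is cheap enough to be worth making.

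**What to change.** In section 6.1:

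1. State which mortality each analysis addresses. Report 30-day mortality as a count with an exact 95% interval and no risk-factor model. The asymptotic interval is unsuitable at such rates: 1.00% ± 1.71% has a lower limit below zero.
2. For death over longer follow-up, replace the logistic models with Cox models for time from first TACE to death. Use the same candidate factors, censor at the last date known alive, and report hazard ratios with 95% confidence intervals.
3. State that vital status is followed after progression, so that censoring in both the Cox and Kaplan-Meier analyses is not driven by prognosis.

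Also reconcile the follow-up length in the Summary with that in section 4.2.

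Cost: mostly SAP wording. Kaplan-Meier already needs the dates, and the planned software, SAS 9.4, fits Cox models. The proportional-hazards assumption must be checked, and vital status after progression must be recorded, which may add some data collection where sites do not already do so.

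### Section 6.1 sets out to identify mortality risk factors with one-covariate models and unadjusted log-rank tests only, so correlated prognostic markers cannot be separated

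*Combined protocol and SAP*

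**What the plan says.** Section 6.1 is the whole analysis plan. On mortality it says: "To identify risk factors related to mortality, univariate logistic regression models will be constructed". On complications: "Univariate analysis is planned to identify variables related to developing complications, using Chi-square tests". On survival: "For survival analysis, Kaplan-Meier curves will be plotted, and log-rank tests are going to be used to evaluate differences between the curves". It sets a threshold of p<0.05 with 95% intervals. The only sentence that could hint at wider modelling is "All effects are considered", which names no model and no covariate.

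No multivariable logistic, Cox or stratified analysis, covariate list or adjustment rule appears anywhere in the document. Section 6.1 also does not say which variables enter the mortality models, or whether mortality there means death within 30 days or within 2 years.

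Section 5.1 lists the patient and disease variables collected. They include "age, gender, etiology of liver disease, diagnosis of HCC, previous nodules treated with surgery, ablation or TACE" and "Child-Pugh score, BCLC stage of the tumor, size, location and number of patients. nodules"; I read the last item as number of nodules. Segmental portal vein invasion and relevant comorbidities are also recorded. Two-year overall survival is a secondary objective (1.2 Secondary Objectives).

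**The concern.** A one-covariate model can show that a marker is associated with death. It cannot show whether the association belongs to that marker or to another that travels with it. The plan's wording goes beyond description: it aims to identify risk factors and attaches a significance threshold.

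The case mix makes this more than a formality. Section 3.1 pools BCLC stage B patients, stage 0 or A patients who cannot have or decline radical treatment, candidates for down-staging, and patients on a transplant waiting list. These groups can be expected to differ in tumour extent, age, comorbidity and access to transplant. Stage, size, number of nodules and liver function are therefore likely to be correlated with one another and with survival.

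If the logistic models are applied to 2-year death there is a second problem. Section 4.2 allows review to end at progression or loss to follow-up, so 2-year status may be unknown for some patients. A logistic model must drop or misclassify them.

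At stake is the credibility of any list of risk factors that comes out of the study, not its primary safety estimates.

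**Working it through.** **The plan's own figure.** Section 6.2 states a precision of 1.71% for an event proportion of 1.00% with 130 patients and a two-sided 95% asymptotic interval. Check: 1.96 × √(0.01 × 0.99 / 130) = 0.0171. It reproduces. It says nothing about modelling, but it supplies the only event rate in the document.

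**30-day mortality.** Using that generic 1% as an assumed rate, expected deaths = 130 × 0.01 = 1.3. The probability of no deaths at all = 0.99^130 = 0.27, and of two or fewer is 0.86. At 10 events per parameter this supports 1.3 / 10 = 0.13 parameters. No model is workable, adjusted or not.

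**2-year overall survival.** The document gives no expected survival, so 80% to 50% is an assumption. Deaths = n × (1 − survival). The number of covariates is deaths / 10, rounded down; one per 10 deaths is a rule of thumb. Section 6.2 gives n = 130, and section 2 gives 100 to 150.

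| Assumed 2-year survival | n = 100: deaths (covariates) | n = 130: deaths (covariates) | n = 150: deaths (covariates) |
|---|---|---|---|
| 80% | 20 (2) | 26 (2) | 30 (3) |
| 70% | 30 (3) | 39 (3) | 45 (4) |
| 60% | 40 (4) | 52 (5) | 60 (6) |
| 50% | 50 (5) | 65 (6) | 75 (7) |

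These counts assume complete follow-up. Losses reduce the observed deaths and so the number of covariates. A small adjusted model is feasible across the range, but three covariates are not guaranteed: 26 deaths allow two.

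**What lack of adjustment can do.** Illustrative simulation, 1000 runs per setting, n = 130. One marker truly affects death (odds ratio 2 or 3 per SD). A second has no effect of its own but is correlated with the first. Deaths are 30% or 50%. All of these values are assumptions. The table shows how often the second marker reaches p<0.05.

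| Correlation | One-covariate logistic model | Both markers in the model | Median unadjusted odds ratio per SD |
|---|---|---|---|
| 0 | 4–6% | 4–6% | 1.0 |
| 0.3 | 17–32% | 4–5% | 1.2–1.3 |
| 0.5 | 37–71% | 4–6% | 1.4–1.6 |
| 0.7 | 64–96% | 4–5% | 1.6–2.0 |

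With no correlation the univariate test holds its nominal level. The excess arises only as the markers become correlated. The log-rank comparisons were not simulated; they are unadjusted too, so they have the same weakness in kind.

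**The case against.** The strongest objection concerns which outcome is meant. Wherever the document names mortality as a study outcome it is early or treatment-related: 1.1 Primary Objective, section 5.1 and section 7.3. The long-term outcome is called overall survival and has its own sentence in 6.1. On that reading the logistic models are for 30-day death, where at about 1.3 expected deaths an adjusted model is no remedy. This stands, and it limits the point. A reader might infer that 6.1 plans logistic models of 2-year death; the text does not say so. The adjusted model proposed here is for overall survival only, where the log-rank comparisons are in any case unadjusted.

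Second, the study calls itself observational and descriptive (3.4, 6.2), finding risk factors is not a listed objective, and an unadjusted association is a legitimate quantity if labelled as one. That is fair, and it keeps the priority low. It does not answer the aim that 6.1 itself states.

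Third, the plan does not list the variables to be tested. Naming stage and liver-function markers is an inference from section 5.1.

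Two stronger readings are tempting and unsupported. A reader might infer that Child-Pugh score, BCLC stage, tumour size and nodule count overlap by construction. The document does not describe how either classification is built, and the limits of Child-Pugh B7 and ECOG 0–1 in section 3.2 narrow the range and may weaken the correlation. A reader might also infer that a device or technique variable could be wrongly credited with an effect. The patient and disease variables in 5.1 include none, and the study has one device in one bead size.

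Finally, a model with two or three covariates cannot settle every question about related markers. That also stands.

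**Conclusion.** The point holds as a low-priority improvement. Section 6.1 aims to identify mortality risk factors but offers only one-covariate logistic models, with unadjusted log-rank tests for overall survival. Collected markers that are likely to be correlated can each be flagged at p<0.05, and the plan has no means of separating them. Any logistic model of 2-year death would also ignore censoring.

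Under the assumed effects and death rates, a marker with no effect of its own is flagged in 17–32% of univariate analyses at correlation 0.3 and in 64–96% at 0.7, instead of about 5%. The document gives no correlations, effect sizes or survival rate, so these figures show the mechanism and do not predict this study's results.

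A small adjusted model is feasible for 2-year overall survival: about 2 to 6 covariates from 26 to 65 deaths in 130 patients, if survival is 80% to 50%. It is not feasible for 30-day mortality at around 1%. The document does not say that univariate findings will be presented as independent or causal. The defect is that nothing in the plan prevents it.

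**What to change.** Amend section 6.1 in three places.

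1. State which mortality is meant. Report 30-day mortality descriptively, with an exact 95% confidence interval and no risk-factor modelling.
2. For 2-year overall survival, keep the univariate results but label them unadjusted associations. Add one prespecified multivariable Cox model. Enter covariates in a fixed order, each as a single term (for example Child-Pugh score, then tumour size, then number of nodules), and stop at one per 10 observed deaths. With 26 deaths only the first two would enter.
3. Describe as independent risk factors only those that the adjusted model supports.

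The cost is a few lines of text and one extra model on data already collected, with no new visits or forms. The downsides are wider intervals, a short covariate list that must be fixed in advance, and possible residual confounding from markers left out. The Cox model also relies on censoring being unrelated to prognosis, so vital status should be sought for patients whose review ends at progression.
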